4.2.9.4 Handling of Dropouts and Missing Data

Missing components required for the determination of chronic target PN pain palliation may result if there is:

- Missing average cycle chronic PN pain intensity score for a specific cycle, that is, patients does not have at least 4 out of 7 PAINS-pNF chronic target PN pain intensity scores in at least 3 non-overlapping 7-day periods (same definition as for 1st key secondary endpoint; see Section 4.2.2.1.2);

and/or

- Missing pain medication:
 - 1) For eDiary, missing chronic PN pain medication for all days* (i.e., 28-day cycle) in that specific cycle.
 - 2) For investigator assessment, missing eCRF investigator assessment of analgesic use at that specific cycle.

*For the purposes of this analysis, pain medication data are considered missing *for a day* if the gatekeeper item “Did you take any medication for your usual (chronic) tumour pain from the time you went to bed last night until now (including overnight)?” is “yes” but no pain medications have been entered or the gatekeeper item is missing.

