Following the identification of the strongest drug class in chronic PN pain medication at each cycle, the change in score at each cycle compared to baseline will be programmatically identified following the algorithm outlined in Figure 3. If changes in the strongest drug class from baseline do not follow under the categories of Figure 3. of “Increased” or “Decreased,” the category “No Change” will be assigned. For the cycles where no PN chronic medication has been recorded in the eDiary, the change will be set to “Missing”.

A secondary definition for change from baseline in PN pain medication (Increased/Decreased/No Change) is derived using the investigator analgesic requirement assessment recorded on the e-CRF, indicating whether the reason is PN pain or other pain.

Figure 3: PN Pain Medication Score Changes Algorithm

PN, plexiform neurofibroma; WHO, World Health Organisation.

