4.2.9 Chronic Target PN Pain Palliation During the Randomised Period

4.2.9.1 Definition

Chronic target PN pain palliation at a cycle is defined as the occurrence of both of the following events:

- 1) Improvement of ≥ 2 in average PAINS-pNF chronic target PN pain intensity score
- 2) No increase in chronic PN pain medication compared to baseline for that cycle
 - i. Assuming that the patient had non-missing chronic PN pain medication data (see Section 4.2.9.4 for definition of “missing”) and did not meet the criteria of eDiary chronic PN pain medication score increase of ≥ 1 compared to baseline (primary definition; see Section 4.2.9.2).
 - ii. Assuming that the patient had non-missing chronic PN pain medication data (see Section 4.2.9.4 for definition of “missing”) and did not meet the criteria of eDiary chronic PN pain medication score increase of ≥ 0.5 compared to baseline (first sensitivity definition; see Section 4.2.9.2).
 - iii. Assuming that the patient had a non-missing investigator electronic case report form (eCRF) assessment (see Section 4.2.9.4 for definition of “missing”) and did not meet the criteria of “increased” due to “PN pain” compared to baseline (second sensitivity definition; see Section 4.2.9.2).

Table 14 summarises the chronic target PN pain definitions that will be examined.

Table 14: Definitions of Chronic Target PN Pain Palliation

Definition	Chronic target PN pain intensity threshold for palliation	Non-missing pain medication data and pain medication increase based on
Primary	2	eDiary chronic PN pain medication score increase of ≥ 1
Sensitivity 1	2	eDiary chronic PN pain medication score increase of ≥ 0.5
Sensitivity 2	2	Investigator’s assessment of “increased” “due to increased PN pain”
Sensitivity 3	From psychometric work*, if different than 2	eDiary chronic PN pain medication increase of ≥ 1
Sensitivity 4	From psychometric work*, if different than 2	eDiary on chronic PN pain medication score of ≥ 0.5
Sensitivity 5	From psychometric work*, if different than 2	Investigator’s assessment of “increased” “due to increased PN pain”

PN, plexiform neurofibroma.

*Psychometric validation of the PAINS-pNF instrument in this study will be performed based on blinded data before DCO1, and a clinically meaningful within-patient change will

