4.2.9.2 Derivations

Detailed derivations for PAINS-pNF chronic target PN pain intensity average cycle score is defined in Section [4.2.2.1.2](#).

An increase in eDiary-reported chronic PN pain medication per cycle compared to baseline is defined as one of the following:

Primary definition: Increase from baseline ≥ 1 point (increase to a stronger class of analgesic medication on the WHO modified analgesic ladder [see Section [3.3.8](#), Table 2]) with the same drug of the strongest score taken for at least 3 days in a 28-day cycle (refer to Section [3.3.8](#),

- [Figure 3](#)).
- Sensitivity definition 1: Increase from baseline ≥ 0.5 point (increase to a stronger class of medication on the WHO modified analgesic ladder [see [Section 3.3.8 Table 2](#)] or an increase in the daily dose or number of pain medications within the same analgesic class) with the same drug taken for at least 3 days in a 28-day cycle (refer to [Section 3.3.8](#),

- [Figure 3\)](#)
- Sensitivity definition 2: “No increase in PN pain medication at a specific cycle compared to baseline” will be identified as those patients who had available eCRF data on investigator assessment of analgesic requirement but did not have an investigator’s assessment of “increased” analgesic requirement “due to PN pain”.

Following the definitions in Section [4.2.9.1](#), chronic target PN pain palliation values will be 1 for patients experiencing pain palliation and 0 for patients that do not.

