4.2.11.4 Handling of Dropouts and Missing Data

For the chronic PN pain medication based on the eDiary, the strongest class of pain medications reported over the 28 days of each cycle will be based on observed scores, that is, days with missing information will be ignored in the derivation.

For purposes of the analysis of decrease in pain medication, 1) if the pain medication data provide sufficient evidence to rule out a decrease for a cycle (see Section 4.2.9.2), that cycle is considered not to have missing pain medication data; 2) if, due to missing *daily*

pain medication data as defined in Section 4.2.9.4, the cycle does not provide sufficient evidence to rule out either an increase or a decrease in pain medication for a cycle, that cycle will be considered to have missing pain medication data.

For the investigator's assessment of change in pain medication, analyses will be based on observed data.

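### Pain palliation: a cycle with only 1 or 2 usable medication-diary days cannot show an analgesic increase, yet it counts as non-missing and can be scored as palliation

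*SAP*

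**What the plan says.** SAP 4.2.9.1 builds the medication component as a default. A participant has no increase if two conditions hold: "Assuming that the patient had non-missing chronic PN pain medication data", and the participant "did not meet the criteria of eDiary chronic PN pain medication score increase of ≥ 1 compared to baseline". The first sensitivity definition has the same form with a threshold of 0.5.

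SAP 4.2.9.2 sets the evidence needed for an increase. The primary definition asks for a step up the modified ladder "with the same drug of the strongest score taken for at least 3 days in a 28-day cycle". Sensitivity definition 1 also admits a higher dose or more drugs within a class, but again "with the same drug taken for at least 3 days in a 28-day cycle".

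SAP 4.2.9.4 says when the component is missing for a cycle: "For eDiary, missing chronic PN pain medication for all days* (i.e., 28-day cycle) in that specific cycle". A single day is missing if the gatekeeper question is answered yes "but no pain medications have been entered or the gatekeeper item is missing".

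SAP 4.2.9.5 uses this rule to decide which assessments are evaluable, both at baseline and after it, and adds no minimum number of medication days. The pain-score component does have a floor in SAP 4.2.2.1.2: at least 4 daily scores in at least 3 non-overlapping 7-day periods after baseline, and in at least 2 such periods at baseline. Time to palliation (SAP 4.2.10.1) takes over the palliation definitions unchanged.

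**The concern.** The threshold for having data is one day, while the threshold for showing an increase is three. Between the two, the result is fixed by the rule and not by what the participant took. Days on which the participant reports taking medication but lists no drug are treated as missing, so evidence of analgesic use is set aside while the cycle can still default to no increase.

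The medication component is there to stop pain relief from a stronger analgesic being credited to study treatment. In a sparsely recorded cycle it does not do so: a step-up that itself lowers the pain score by 2 points can pass as palliation. Time to palliation is exposed as well, because one such cycle is enough to create the event.

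**Working it through.** The plan gives no sample size, power or event rate for palliation, so there is no stated figure to reproduce. The check concerns how the rules combine, followed by an illustration of size.

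**Step 1: the rules side by side.** Let m be the number of usable medication days in a 28-day cycle.

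- m = 0: the component is missing (SAP 4.2.9.4).
- m = 1 or 2: the component is non-missing, but at most 2 days of a stronger drug can be seen, below the 3 required (SAP 4.2.9.2). The result is no increase with certainty, even if the stronger drug was taken on all 28 days.
- m = 3 or more: an increase can be detected, but only if at least 3 of its days are among those recorded.

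A palliation value of 1 also needs a valid pain score, hence at least 4 × 3 = 12 pain-diary days. The affected cycles are therefore those in which the pain item is completed and the medication items largely are not.

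**Step 2: other rules that might close the gap.** SAP 3.3.8 says "For the cycles where no PN chronic medication has been recorded in the eDiary, the change will be set to" missing. That applies only when nothing was recorded; a cycle with one recorded drug day is outside it and otherwise falls to the no-change category. The pain-score floor governs pain scores only. Sensitivity definition 1 keeps the 3-day requirement.

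**Step 3: size under partial completion.** Assumption: the m recorded days are a random subset of the 28, and the stronger drug is taken on K of the 28. Neither K nor m comes from the documents, so ranges are shown.

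P(detect) = 1 − Σ (x = 0 to 2) C(K, x) · C(28 − K, m − x) / C(28, m)

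For K = 7 and m = 12, C(28, 12) = 30,421,755 and the three terms are:

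- x = 0: 293,930 / 30,421,755 = 0.010
- x = 1: 7 × 352,716 / 30,421,755 = 0.081
- x = 2: 21 × 352,716 / 30,421,755 = 0.243

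Unrounded, the terms sum to 0.334, so P(detect) = 0.666.

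Probability (%) that a true step-up is classed as an increase:

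| Recorded days m | K = 3 | K = 5 | K = 7 | K = 14 | K = 28 |
|---|---|---|---|---|---|
| 1 or 2 | 0 | 0 | 0 | 0 | 0 |
| 4 | 0.1 | 1.1 | 3.8 | 29.8 | 100 |
| 8 | 1.7 | 12.3 | 30.6 | 89.6 | 100 |
| 12 | 6.7 | 35.7 | 66.6 | 99.7 | 100 |
| 20 | 34.8 | 87.7 | 99.1 | 100 | 100 |
| 24 | 61.8 | 98.9 | 100 | 100 | 100 |

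The row m = 24 is close to the 85% compliance flag in Protocol 8.1.8.9 (0.85 × 28 = 23.8 days). At that level only very short step-ups are missed.

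**Step 4: direction.** After baseline, an unrecorded day can only hide stronger-drug use, so misclassification moves a cycle towards no increase. At baseline the same all-days rule can miss the strongest drug in use. Unchanged treatment then looks like an increase later and palliation is scored 0.

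**The case against.** The strongest reply is that the extreme case is narrow. Pain and medication are entered daily on one hand-held device (Protocol 8.1.8.9), and site staff pre-populate the drug list and review it at visits (Protocol 8.1.8.3). A cycle with at least 12 pain days but only 1 or 2 medication days should be unusual. The analysis is also repeated with the investigator's assessment of analgesic requirement, which does not use the eDiary and is scheduled every cycle to Cycle 12. SAP 4.1.1.2 tabulates medication-diary completion by cycle and arm. Palliation is outside the multiplicity procedure.

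All of this stands and limits the point, but none of it changes the primary definition. The completion tables give rates per cycle and arm. The breakdown by number of adequately completed 7-day periods is specified for pain scores only, so the tables need not show how many participant-cycles are sparse.

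A reader might also infer that SAP 4.2.11.4 already holds the right rule and need only be extended. That section makes a cycle missing when "the cycle does not provide sufficient evidence to rule out either an increase or a decrease in pain medication for a cycle". But it is written for the medication-decrease analysis, and its first clause keeps any cycle that rules out a decrease, whether or not an increase is ruled out. Turned into a strict test of whether missing days could bring the count to 3, it would need 28 − 2 = 26 recorded days (93%). A participant with 24 of 28 days (85.7%) and no step-up would be lost. Read literally, it would also set to missing a cycle in which 3 step-up days had been seen.

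**Conclusion.** The gap is real on the text as printed. With 1 or 2 usable medication days a post-baseline cycle cannot show an increase under the primary definition or sensitivity definition 1. It is still evaluable, and it counts as palliation if the pain score has fallen by 2 points. With more recorded days the effect is graded: for 7 step-up days, 67% detection at 12 recorded days and 99% at 20, assuming random recording. These are detection probabilities, not a bias in the odds ratio.

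Two stronger readings are not supported. One is that the error always favours response: that holds for post-baseline cycles, but the baseline rule can push the other way. The other is that the result is tilted towards selumetinib. The documents give neither the frequency of sparse cycles nor any difference between arms, and if hidden step-ups were commoner on placebo the bias would run against selumetinib.

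The increase algorithm is also referred to Figure 3 of SAP 3.3.8, which is not shown in the available text, so a further rule there could not be checked. This is a worthwhile and cheap correction to a secondary endpoint, not a threat to the confirmatory analyses.

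**What to change.** In SAP 4.2.9.4, treat eDiary medication as non-missing for a cycle only if there are at least 4 usable medication-diary days in at least 3 non-overlapping 7-day periods, and in at least 2 such periods at baseline, matching the pain-score rule. Add that a post-baseline cycle in which at least 3 days of a stronger drug are already recorded is classed as an increase whatever its completeness. Apply both to the primary definition, the eDiary-based sensitivity definitions and time to palliation. Keep the current all-days rule as a sensitivity analysis. Do not make the strict evidence rule the primary one.

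The cost is SAP wording, one derivation change and somewhat fewer evaluable participant-cycles. The floor reduces misclassification but does not remove it: at the 12-day minimum, detection is still only about 36% for 5 step-up days. Retaining sparse cycles only when they show an increase also leans slightly towards non-response, which is a further reason to report the current rule alongside.

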4.2.9.5 Primary Analysis of Chronic Target PN Pain Palliation

The pain palliation response during the randomised period is analysed using a random-effect logistic regression model including treatment, geographical region, and cycle number as fixed effects; baseline chronic target PN pain intensity score and baseline

chronic PN pain medication modified WHO analgesic ladder score as covariates; and the following interaction terms: treatment-by-cycle number, baseline chronic target PN pain intensity score-by-cycle number, and baseline chronic PN pain medication score-by-cycle number.

The analysis will be conducted using PROC GLIMMIX in SAS with a random intercept also included to account for variability between patients. Random (subject-specific) effects will be not explicitly modelled, and an unstructured covariance matrix will be used to model the within-patient correlations between the repeated measurements and to allow for unequal treatment variance. An unstructured modelling of within-patient correlations removes one layer of assumptions on the random effects and often provides the best fit to the data.

If the fit of the unstructured covariance structure fails to converge, every attempt should be made to ensure that convergence is obtained from the unstructured correlation structure. Parameters will be tried to be estimated by means of the Fisher's scoring algorithm rather than the default Newton-Raphson algorithm. If convergence is still not reached after the change in the interaction algorithm, a more parsimonious model will be implemented using one of the following covariance structures in order until convergence is reached: toeplitz with heterogeneity, autoregressive with heterogeneity, toeplitz, autoregressive, and compound symmetry. All main effects and the interaction terms will remain in the model, regardless of significance.

The results of the analysis are presented in terms of an odds ratio (selumetinib versus placebo) together with its 95% CI and p-value at each cycle of the randomised period (estimated using the treatment-by-cycle interaction coefficient) and overall, over the randomised period (based on the treatment coefficient). For each treatment arm, the odds will be presented along with the number of non-missing observations used in the estimation (n), the observed number and percentage of responder, and the corresponding 95% CI.

The analysis will be performed on a subset of the Pain FAS population with evaluable baseline assessments and at least one evaluable post-baseline assessment. An evaluable baseline assessment is defined as having both baseline PAINS-pNF chronic target PN pain intensity score (same definition as the 1st key secondary endpoint; refer to Section 4.2.2.1.2) and non-missing pain medication (refer to Section 4.2.9.4 for missing pain medication derivation). An evaluable assessment at baseline or a specific cycle is defined as having both average chronic target PN pain intensity score (same definition as the 1st key secondary endpoint; refer to Section 4.2.2.1.2) and non-missing pain medication (refer to Section 4.2.9.4 for missing pain medication derivation).

This analysis will be repeated using both sensitivity definitions outlined in Section 4.2.9.2. For the sensitivity using investigator assessment of analgesic use, the random-effect logistic

regression model will include treatment, geographical region, and cycle number as fixed effects; baseline chronic target PN pain intensity score and baseline chronic PN pain medication score as covariates; and the following interaction terms: treatment-by-cycle number, baseline chronic target PN pain intensity score-by-cycle number, and baseline chronic target PN pain medication score-by-cycle number.

